2.6.1.3 Absolute change in LIC measured by MRI from baseline over time

Absolute changes from baseline LIC at all scheduled LIC evaluation weeks will be analyzed. Patients without any LIC post-baseline value at or prior to the scheduled LIC evaluation week had missing values and will be not included in the analyses for the scheduled weeks. Descriptive statistics and box plots will be provided for:

- LIC at baseline, at all scheduled LIC evaluation weeks (24, 52, 76, 104, 128, 156, 180, 208, 232, 260) and for last available LIC measurement
- Absolute change from baseline LIC at all scheduled LIC evaluation weeks (24, 52, 76, 104, 128, 156, 180, 208, 232, 260) and for last available LIC measurement.

2.6.1.4 Absolute change in LIC measured by MRI from baseline over time by underlying disease

Absolute changes from baseline LIC at all scheduled LIC evaluation weeks will be analyzed by underlying disease. Patients without any LIC post-baseline value at or prior to the scheduled LIC evaluation week had missing values and will be not included in the analyses for the scheduled weeks.

Descriptive statistics will be provided for:

- LIC at baseline, at all scheduled LIC evaluation weeks (24, 52) and for last available LIC measurement in treatment year 1;
- Absolute change from baseline LIC at all scheduled LIC evaluation weeks (24, 52) and for last available LIC measurement in treatment year 1.

2.6.1.5 Absolute change in SF from baseline over time

Baseline serum ferritin as average of all available ferritin values from screening to last sample prior to or on the day of first intake of study medication;

Descriptive statistics and box plots will be provided for:

- SF at baseline, quarterly SF up to week 260;
- Absolute changes of quarterly SF at quarter 1, 2, ..., 20 from baseline.

Quarter is defined as average of available ferritin values from visit corresponding to end of quarter, visit prior, and visit after (e.g. end of first quarter includes average ferritin values from Visits 11, 12, and 13).

Absolute change from baseline at week 52 will be tested using a 2-sided one sample t-test. The p-value will be considered as exploratory with no multiplicity considerations.

2.6.1.6 Correlation between serum ferritin and LIC at baseline and EOS

Scatter plots with pearson correlation coefficient and simple linear model will be provided without imputing any missing data:

- LIC versus serum ferritin at baseline, Week 24, Week 52, Week 104, Week 156, Week 208, Week 260
- LIC versus serum ferritin at baseline, Week 24, Week 52, Week 104, Week 156, Week 208, Week 260 on log scale
- Absolute changes in LIC versus absolute changes in serum ferritin at baseline, Week 24, Week 52, Week 104, Week 156, Week 208, Week 260

2.6.1.7 Medical Outcomes Study Short Form-36 (SF-36)

The Medical Outcomes Study Short Form 36 (SF-36v2) is a self-administered questionnaire for adults (greater than 18 years of age) and contains 36 items which measure eight dimensions: Physical functioning (10 items), Role limitation due to physical health problems (4 items), Bodily pain (2 items), General health perceptions (5 items), Vitality (4 items), Social functioning (2 items), Role limitations due to emotional problems (3 items) and General mental health (5 items). There is an additional single item giving information on health change over the past year. Item scores for each dimension are coded, summed and transformed to a scale from 0 (worst possible health state measured by the questionnaire) to 100 (best possible health state). The higher values indicate a better evaluation of health. Two summary scores of physical and mental health can also be calculated and scoring is normbased, with normative values at 50 and no floor or ceilings. In addition, the SF-6D, a utility measure of health states, can be derived

from the SF-36 and the scoring for the SF-6D utility values will also be assessed using the scoring methods from the developers.

Descriptive statistics will be provided for all dimensions, PCS/MCS summary scores and SF-6D scores (including absolute change from baseline) by visit (baseline, week 52, 104, and 156).

Absolute change from baseline at week 52, 104, and 156 will be tested as exploratory using a 2-sided one sample t-test. P-values will be considered as exploratory with no multiplicity considerations.

2.6.1.8 Pediatric Quality of Life Questionnaire

The PedsQL™ is a modular approach to measuring health-related quality of life (HRQOL) in children and adolescents. This will be administered to children between the ages of 13 to 18 years. The approach includes both a child self-report and parent proxy-report. The 23-item PedsQL™ Generic Core Scales encompass the essential core domains for pediatric HRQOL measurement: 1) Physical Functioning (8 items), 2) Emotional Functioning (5 items), 3) Social Functioning (5 items), and 4) School Functioning (5 items). The Generic Core Scales are designed to enable comparisons across patient and healthy populations.

Scores are transformed on a scale from 0 to 100. Items are reversed scored and linearly transformed to a 0-100 scale as follows: 0=100, 1=75, 2=50, 3=25, 4=0.

- Score by Domains: If more than 50% of the items in the scale are missing, the scale scores should not be computed,

Mean Score of domain = Sum of the items in the domain over the number of items answered in that domain.

- Psychosocial Health Summary Score = sum of the items over the number of items answered in the Emotional, Social, and School Functioning Scales
- Physical Health Summary Score = Physical Functioning Scale Score
- Total Score = Sum of all the items over the number of items answered on all the scales.

If more than 50% of the items in the scale are missing, the Scale Scores should not be computed. If 50% or more items are completed: Impute the mean of the completed items in a scale.

Descriptive statistics will be provided for all domains scores (including absolute change from baseline) by visit (baseline, week 52, 104, and 156).

Absolute change from baseline at week 52, 104, and 156 will be tested as exploratory using a 2-sided one sample t-test.

P-values will be considered as exploratory with no multiplicity considerations.

2.6.1.9 Endocrine function

The endocrine function will be assessed using the following parameters: Total and Free testosterone (males), LH and FSH (females), TSH, total and free T4, total and free T3, fasting plasma glucose, insulin, insulin resistance, and cortisol. Insulin resistance will be derived by HOMA method:

Insulin resistance= fasting Glucose (mmol/L) x fasting Insulin (mU/L) / 22.5

Descriptive statistics will be provided for the values of all parameters and also for their corresponding absolute change from baseline by scheduled visits (Week 12, 24, 36, 52, 64, 76, 88, 104, 116, 128, 140, 156, 168, 180, 192, 208, 220, 232, 244 and 260)

2.7 Safety analyses

All safety analyses will be based on the Safety Set. Post-baseline safety data included values up to 30 days after last non-zero dose.

2.7.1 Adverse events (AEs)

AEs and the principal cause of death will be coded using MedDRA 20.1.

All summaries of AEs only included treatment emergent AEs, i.e., AEs which started or worsened on or after the day with first study medication intake and not more than 30 days after last study medication.

The incidence of AEs (number and percentage of patients with AEs) will be summarized by MedDRA primary SOC and preferred term, and separately by preferred term only. These two summaries will be generated for all AEs, serious AEs (SAEs), AEs with suspected relationship to study medication, SAEs with suspected relationship to study medication, AEs leading to discontinuation of study medication, and AEs leading to dose adjustment or interruption. AEs will be also summarized by MedDRA primary SOC, preferred term, and maximum severity. Non-serious AEs (i.e. excluding SAEs) will be also summarized by primary SOC and preferred term.

2.7.1.1 Adverse events of special interest / grouping of AEs

Specific groupings of adverse events of special interest will be considered and the number of patients with at least one event in each grouping will be reported. Such groups consist of adverse events for which there is a specific clinical interest in connection with Deferasirox treatment. Note that certain adverse events may be reported within multiple groupings/AESIs.

AESIs are defined by MedDRA terms. Definition for retrieval (maintenance of terms considered AESI) is in a separate document in the Novartis Documentum management system at the path “CREDI Projects/I/ICL670A/Integrated Medical Safety”. The latest document has to be used (The name of the retrieval document should be “ICL670 AESI_MedDRA xx.x_DDMmmYY”, where xx.x is the MedDRA version number. At the time of approval of this report analysis plan, the latest retrieval document is “ICL670 AESI_MedDRA 20.1_08Nov17”). The MedDRA codes will be used to generate the outputs.

For adverse event started before and ended after one-year cutoff date, the end date of the adverse event would be set as “missing”, but reported as “Ongoing” in listings.

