Mean SF significantly decreased at one year: -121 ng/mL (95% CI: -203, -38) and -222 ng/mL (95% CI: -304, -140) for deferasirox 5 and 10 mg/kg/day groups while there was an increase in the placebo (115 ng/mL: 95% CI: 33, 196); difference vs placebo was significant (-235 ng/mL, $P<0.001$ and -337 ng/mL, $P<0.001$ for deferasirox 5 and 10 mg/kg/day, respectively).

Overall AE rates were 80.4, 76.4 and 78.2% in the placebo, deferasirox 5 and 10 mg/kg/day groups; respectively. The most common investigator-assessed drug-related AEs in the overall placebo (n=56), deferasirox 5 and 10 mg/kg/day groups, respectively, were nausea (7.1, 5.5 and 7.3%), rash (1.8, 3.6 and 9.1%), diarrhea (1.8, 0 and 9.1%), headache (3.6, 3.6 and 1.8%) and upper abdominal pain (0, 3.6 and 1.8%). Serious AEs were reported in 14.3, 12.7 and 16.4% of patients in the placebo, deferasirox 5 and 10 mg/kg/day groups, respectively. Three (5.5%) deferasirox-treated patients (deferasirox 10 mg/kg/day) had 2 consecutive serum creatinine level increases $>33\%$ above baseline and $>$ upper limit of normal (ULN). One patient in the placebo group had an ALT increase >5 x ULN and >2 x baseline and 2 patients had an AST increase to >5 xULN and > 2 x baseline, 1 in the deferasirox 10 mg/kg/day and 1 in the placebo group (Taher 2012).

Therefore, in patients with NTDT and iron overload, deferasirox at starting doses of 5 and 10 mg/kg/day with dose escalation up to 20 mg/kg/day reduced iron overload, as evidenced by significant decreases in LIC and SF and with an overall safety profile comparable to placebo (Ta^her 2012). The reduction in LIC was shown to be dose-dependent since the reduction in LIC by average actual dose showed that patients who received deferasirox $>12.5\text{--}\leq 17.5$ mg/kg/day achieved the greatest LIC decrease, followed by the $\geq 7.5\text{--}\leq 12.5$ mg/kg/day subgroup and the $>0\text{--}<7.5$ mg/kg/day subgroup. Patients who had their dose doubled to 20 mg/kg/day achieved greater reductions in LIC compared with patients who remained on the 10 mg/kg/day starting dose (Ta^her et al. 2013). Continued treatment with deferasirox at appropriate doses for up to 2 years resulted in a progressive reduction in iron overload; mean change -7.14 mg Fe/g dry weight (dw) (mean dose 9.8 ± 3.6 mg/kg/day; Ta^her 2013).

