8.1 Adverse events

8.1.1 Definitions and reporting

An adverse event is defined as the appearance of (or worsening of any pre-existing) undesirable sign(s), symptom(s), or medical condition(s) that occur after patient's signed informed consent has been obtained. Abnormal laboratory values or test results occurring after informed consent constitute adverse events only if they induce clinical signs or symptoms, are considered clinically significant, require therapy (e.g., hematologic abnormality that requires transfusion or hematological stem cell support), or require changes in study medication(s).

Adverse events that begin or worsen after informed consent must be recorded in the Adverse Events CRF. Conditions that were already present at the time of informed consent must be recorded in the Medical History CRF. Adverse event monitoring must be continued for at

least 30 days following the last dose of study treatment. Adverse events (including lab abnormalities that constitute AEs) should be described using a diagnosis whenever possible, rather than individual underlying signs and symptoms. When a clear diagnosis cannot be identified, each sign or symptom must be reported as a separate Adverse Event.

Severity of adverse events will be assessed as mild, moderate, or severe. Information about deaths will be collected through a Death form.

The occurrence of adverse events must be sought by non-directive questioning of the patient (subject) during the screening process after signing informed consent and at each visit during the study. Adverse events also may be detected when they are volunteered by the patient (subject) during the screening process or between visits, or through physical examination, laboratory test, or other assessments. As far as possible, each adverse event must be evaluated to determine:

1. The severity grade (mild, moderate, or severe)
2. Its duration (Start and end dates)
3. Its relationship to the study treatment (Reasonable possibility that AE is related: No, Yes)
4. Action taken with respect to study or investigational treatment for the adverse event (none, study treatment dose adjusted, study treatment temporarily interrupted, study treatment permanently discontinued, unknown, not applicable)
5. Whether concomitant medication or non-drug therapy was taken for the adverse event (No, Yes)

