- A one-year-analysis which will include assessments and events within treatment Year- 1.
- A final analysis when the study is completed and the last patient enrolled has completed last study visit or discontinued.

Additional information for analysis methods will be available in RAP documentation. In addition to the overall population analysis, it is anticipated that statistical analysis will be performed according to subgroup Chinese/non-Chinese patients.

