Cmax	Maximum (peak) observed plasma concentration after single dose administration
CSR	Clinical Study report
CTCAE	Common Terminology Criteria for Adverse Events
DMC	Data Monitoring Committee
dw	Dry weight
ECG	Electrocardiogram
eCRF	Electronic Case Report/Record Form
EOS	End of study
FAS	Full Analysis Set
FE	Iron
FSH	Follicle stimulating hormone
GGT	Gamma glutamyl transferase
HbE	Hemoglobin E
HbH	Hemoglobin H
LDH	lactase dehydrogenase
LH	Luteinizing hormone
LIC	Liver iron content
LPLV	Last patient last visit
MedDRA	Medical Dictionary for Drug Regulatory Affairs
MRI	Magnetic resonance imaging
NTDT	Non-transfusion-dependent thalassemia
o.d.	Once Daily
OS	Overall Survival
PedsQL™	Pediatric Quality of Life Inventory™
PFS	Progression-Free Survival
PK	Pharmacokinetics
PPS	Per-Protocol Set
PRO	Patient-reported Outcomes
qd	Qua'que di'e / once a day
QoL	Quality of Life
RAP	Report and Analysis Process
RECIST	Response Evaluation Criteria in Solid Tumors
SAE	Serious adverse event

SAP	Statistical Analysis Plan
SD	Standard deviation
SF	Serum ferritin
SF-36	Medical Outcomes study short form-36
SF-6D	Short-Form Six-Dimension
SOC	System Organ Class
THALASSA	Novartis Study CICL670E2209
TFLs	Tables, Figures, Listings
Tmax	Time to reach maximum (peak) plasma concentration after single dose administration
TSH	Thyroid stimulating hormone
WHO	World Health Organization

1 Introduction

CICL670E2419 is a phase IV open label, multi-center, efficacy and safety study of deferasirox in iron overloaded patients with non-transfusion dependent thalassemia. This open-label, single-arm, multi-center 5-year study was designed to evaluate the efficacy and safety of deferasirox in iron overloaded NTDT patients, at least ten-years-old. A 1-year analysis was performed to assess the primary objective and selected secondary objectives. This study enrolled 134 patients including 68 Chinese and 66 non-Chinese, with 112 patients still on treatment at the time of the 1-year primary analysis.

The primary objective of this one-year analysis was met, confirming activity of deferasirox in the NTDT population, as observed in Study ICL670A2209. The absolute change in LIC from Baseline to Week 52 was statistically significantly different (Paired T-test, $p<0.0001$, two-sided). The absolute mean change in LIC (mg Fe/g dw) from Baseline to Week 52 was -6.68 (SD 7.018) with a 95% CI (-7.91, -5.45).

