Pharmacokinetic analysis was performed on the data from 22 patients at Week 4. Mean (SD) AUC_{tau} at 10 mg/kg/day was 773 (350) hr \times μmol/L and was similar for the Chinese and non-Chinese groups (770 (405) and 776 (250) hr \times μmol/L, respectively). Mean (SD) C_{max} was 61 (27) μmol/L and was comparable between these two groups (Chinese 62 (33) μmol/L and non-Chinese 57 (14) μmol/L).

This analysis plan is written to analyze all data up to last patient last visit (LPLV) and to support final CSR.

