2.1.1 General definitions

Observation periods for safety analysis

The overall observation period will be divided into three mutually exclusive segments:

1. pre-treatment period: from day of patient's informed consent to the day before first dose of study medication
2. on-treatment period: from day of first dose of study medication to 30 days after last nonzero dose of study medication.
3. post-treatment period: starting at day 30+1 after last dose of study medication.

Safety summaries (tables, figures) include only data that from the pre-treatment period (to display the baseline status e.g. for ECG) and the on-treatment period, i.e. no data from the post-treatment period must be included if not otherwise requested from Health Authorities. In particular, summary tables for adverse events (AEs) have to include only AEs that started or worsened during the on-treatment period, the so-called treatment-emergent AEs. Similarly, summary tables and figures only include lab values observed during the on-treatment period. However, all safety data (including those from the post-treatment period) will be listed and those collected during the pre-treatment and post-treatment period will be flagged.

The above defined observation periods will be only applicable for safety analysis. In particular, all post-baseline values will be used in the analyses of LIC, serum ferritin [REDACTED] defined in the protocol section 7.2.1 for efficacy assessment.

Study day, last assessment day and baseline

Study day

Since this is an open label study, for all variables (safety or efficacy), study day will be defined as the number of days since the date of first dose of study medication. For a particular date on or after first dose, it is calculated as:

Study day = Assessment date – Date of first dose of study medication + 1.

Therefore, the date of the first dose of study medication will be Day 1 by definition.

The day before this day will be defined to be Day -1, i.e., there is no Day 0. Study days before first dose of study medication will be calculated as:

Study day = Assessment date – Date of first dose of study medication.

In the above study day calculation, the date of the first day of study drug will be replaced with the study drug assignment date if the patient doesn't take any study drug.

So if the patient doesn't take the study drug, Day 1 is the study drug assignment date.

Definition of baseline value

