2.5 Analysis of the primary objective

2.5.1 Primary endpoint

The trial is designed to assess the efficacy of deferasirox in patients with non-transfusion dependent thalassemia based on absolute change in LIC from baseline after one year of treatment. The analysis for primary objective was performed at one-year (data cut-off date : 03-Jan-2015). The study met its primary objective. The primary endpoint, absolute change in LIC (mg Fe/g dw) at Week 52 from baseline, was statistically significantly different from 0 (Paired T-test $p<0.0001$, two-sided). The absolute change in LIC at Week 52 from baseline had mean (SD) -6.68 (7.018) (mg Fe/g dw) and a 95% confidence interval (-7.91, -5.45) (mg Fe/g dw).

As done in previous studies within patients with transfusional iron overload, a normal distribution will be assumed for LIC absolute change.

LIC will be measured at screening (Visit 1), Week 24 (Visit 15) and Week 52 (Visit 25) in treatment year 1. The primary efficacy variable will be the absolute change from baseline in LIC at Week 52, i.e. the difference of LIC at Week 52 minus LIC at baseline.

The absolute change in LIC from baseline after one year of treatment will be analyzed using the FAS set.

The following estimates will be provided:

- point estimate of the absolute change at Week 52,
- the ordinary 2-sided 95% confidence interval,
- p-value (descriptive only).

Also, LIC values at Week 52 will be computed with their corresponding 95% CI.

Handling of missing values/censoring/discontinuations

In case of missing LIC at Week 52, the last available post-baseline LIC value before Week 52 will be used in the calculation of the primary endpoint. Patients without post-baseline LIC at or before Week 52 or baseline LIC will be excluded from the analyses.

Supportive analyses

In order to further assess the absolute change and the relative change in LIC from baseline at Week 52, the estimates and the 95% confidence intervals will be provided for the following proportions (In case of missing LIC at Week 52, the last available post-baseline LIC value before Week 52 will be used):

- The proportion of patients with an LIC decrease by at least 3 mg Fe/g dw from baseline (LIC decrease ≥ 3 mg Fe/g dw) at Week 52; i.e., proportion of LIC decrease ≥ 3 mg Fe/g dw = subjects with $((\text{baseline LIC} - \text{LIC at Week 52}) \geq 3)$ divided by total number of subjects

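### The final-analysis SAP keeps a one-year data-cut rule that blanks recorded AE end dates, so resolved AEs straddling the cut-off would be listed as ongoing

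*SAP*

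**What the plan says.** The last sentence of SAP Section 2.7.1.1 reads: "For adverse event started before and ended after one-year cutoff date, the end date of the adverse event would be set as" missing, with the event displayed as ongoing in listings.

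The SAP Introduction gives the scope of the plan: "This analysis plan is written to analyze all data up to last patient last visit (LPLV) and to support final CSR". The one-year analysis is already in the past. SAP Section 2.5.1 says: "The analysis for primary objective was performed at one-year (data cut-off date : 03-Jan-2015", and this is the only date the SAP labels as a cut-off.

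The protocol separates the two analyses at the start of Section 10. The first is described as "A one-year-analysis which will include assessments and events within treatment Year- 1"; the second is run once the study is complete. For each AE, Protocol Section 8.1.1 asks for "Its duration (Start and end dates", and, as a separate item, the outcome. On listings, SAP Section 2.1.1 says: "However, all safety data (including those from the post-treatment period) will be listed".

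**The concern.** By its own terms the rule applies only to AEs whose end is known to fall after the cut-off. In a report built on data cut at one year, treating such an event as unresolved is correct, because at the cut it was. In a final report the later end date is in the database, and the rule replaces a known fact with a missing value.

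The direct consequence is that resolved AEs appear as ongoing in the final listings, possibly beside a recorded outcome that says they resolved.

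There is a possible second consequence. SAP Section 2.7.4.3 estimates the duration of the first gastrointestinal (GI) event by Kaplan-Meier and censors events without an end. SAP Section 5.1 does not impute missing AE end dates. If the blanked dates feed that analysis, a straddling first event changes from observed to censored at last treatment plus 30 days (SAP Section 2.1.1), which pushes the estimated duration upward. The SAP does not say whether they do.

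**Working it through.** **1. Does anything confine the rule to the one-year report?** No. The sentence carries no such limit and the SAP's stated scope is the final analysis. The same subsection cites an AESI retrieval file for MedDRA 20.1 dated 08Nov17, so it was updated well after January 2015 and the sentence stayed. The protocol contains no matching rule, and SAP Section 4 declares no change from the protocol analyses.

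**2. Effect on one event (assumed dates).** An AE from 20-Dec-2014 to 10-Jan-2015 lasts 22 days and straddles 03-Jan-2015. Under the rule it has no end date and is listed as ongoing. If it were a first GI event and the blanked date were used, its duration would be censored at 223, 773 or 1107 days for assumed last treatment dates of 30-Jun-2015, 31-Dec-2016 or 30-Nov-2017.

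**3. How many listed AEs?** The documents give no count, so this is a range under assumptions.

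- AE rate: Protocol Section 1.2.1.2 reports for the earlier NTDT trial "Overall AE rates were 80.4, 76.4 and 78.2% in the placebo, deferasirox 5 and 10 mg/kg/day groups". Taking 78.2% and a Poisson process over one year, rate = −ln(1 − 0.782) = 1.523 per patient-year.
- Patients at risk: the SAP Introduction reports 134 enrolled, "with 112 patients still on treatment at the time of the 1-year primary analysis".
- Mean AE duration d: not given; 7 to 60 days assumed.

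AEs in progress at the cut-off = 112 × 1.523 × d / 365.25 = 0.467 × d.

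| Mean duration (days) | AEs straddling the cut-off |
|---|---|
| 7 | 3.3 |
| 14 | 6.5 |
| 30 | 14.0 |
| 60 | 28.0 |

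The count scales linearly with the rate and assumes that these events later resolve. If AEs cluster in some patients, the same 78.2% corresponds to a higher mean rate than 1.523.

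**4. GI duration, only if the blanked dates are used.** Protocol Section 1.2.1.2 gives GI disturbances in about 26% of patients (a transfusional population): 0.26 × 134 ≈ 35 first events, all GI groups pooled. Each scenario simulated 400,000 events with exponential durations and 1826 days of treatment. Onset was either uniform over five years or early (exponential, mean 180 days). The cut-off fell at patient day 364, at day 730, or uniformly between them. Events unresolved by day 1856 were censored in both versions; straddling events were recoded as censored at 1856 days minus onset. The table shows the largest effect across scenarios, which came from early onset with the cut-off at day 364.

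| True median (days) | Straddling fraction | Events of 35 | Kaplan-Meier median | Shift (days) |
|---|---|---|---|---|
| 5 | 0.55% | 0.2 | 4.99 → 5.01 | 0.02 |
| 10 | 1.16% | 0.4 | 9.95 → 9.99 | 0.04 |
| 30 | 4.24% | 1.5 | 30.04 → 30.49 | 0.45 |
| 90 | 18.54% | 6.5 | 90.16 → 95.25 | 5.1 |

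The smallest effect at a 90-day median was 1.3 events and a shift of 0.6 day (90.33 → 90.94). Section 1.2.1.2 describes these reactions as mostly transient, so the shorter medians are the more plausible.

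**The case against.** The strongest reply is that this is leftover text that nobody would apply. The SAP retains other one-year wording: Section 2.5.1 specifies the completed primary analysis in the future tense, and Section 2.6.1.4 still summarises treatment year 1. The general provisions point the other way: Protocol Table 10-1 includes all safety events in the final analysis, and the SAP lists all safety data. It probably is leftover. But none of those provisions cancels the sentence, and a programmer who follows the plan would carry it out.

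Three points about reach stand:

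- The one-year cut-off is not defined in Section 2.7.1.1. If it meant each patient's Week 52, which SAP Section 2.1.1 calls the end of treatment year 1, different AEs would be affected but the defect would remain.
- The sentence sits under the AESI heading, though it is worded for any adverse event. On an AESI-only reading, fewer AEs are affected than estimated above.
- AE outcome is collected separately and is not blanked. If it is listed, a reader could see that the event resolved, but the listing would then contradict itself.

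The sizes are also fairly criticised as resting on assumptions. The AE rate comes from another trial with different dosing. Section 2.7.4.3 analyses seven GI groups separately, so 35 pooled events is not the denominator of any planned curve. For diarrhoea alone, the earlier trial's 9.1% drug-related rate at 10 mg/kg/day gives 0.091 × 134 ≈ 12 patients, and 4.24% of 12 is about 0.5 event. The largest shifts are maxima over the scenarios tried, not bounds.

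**Conclusion.** The concern holds, as a minor point. Read as written, the final-analysis plan instructs that known AE end dates be blanked and resolved events be listed as ongoing. That the sentence exists and is unrestricted is certain; its reach depends on what the cut-off means and whether it covers all AEs or only AESIs.

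On the stated assumptions, the final listings would misstate roughly 3 to 28 AEs. Any effect on the GI duration analysis is conditional and probably negligible: under half a day on medians up to 30 days. AE incidence, AESI counts, time to first event, deaths and all efficacy results are unaffected, because none of them uses an AE end date.

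**What to change.** Delete the sentence from SAP Section 2.7.1.1, or confine it explicitly to the one-year report with its 03-Jan-2015 cut-off. Add that the final analysis and listings use AE end dates as recorded, and that only AEs with no recorded end date at final database lock are shown as ongoing and treated as censored in the duration analysis.

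The cost is an edit of one or two sentences and, if the rule has been programmed, removal of that derivation. No new data are needed.
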